12 DATA ANALYSIS AND MONITORING

12.1 SAMPLE SIZE DETERMINATION

This study is designed to have adequate power to test the primary hypotheses that the CTI will result in lower odds of repeat ED use within 30 days of discharge compared to the control group (Hypothesis 2B). Based on published data, we expect 20% of the subjects in the control group to have at least 1 repeat ED visit within the 30-day follow-up period. In order to detect a 5% absolute decrease in the frequency of repeat ED visits with 80% power using a Chi-square test at a two-sided significance level of 5%, we will need 860 subjects per group. We anticipate approximately 25% attrition over the 30-day follow up period. As such, a final sample size of 1200 subjects in each group will be recruited for participation. We also calculated the minimum detectable effect size testing individual biomedical and psychosocial factors predicting repeat ED visit in Aim 4 for intervention group only. With an expected 15% baseline proportion of repeat ED visit, the sample size of 860 in the intervention group will have 80% power to detect an odds ratio (OR) of 1.3 per standard deviation of a normally distributed predictor. Similarly, 80% power is available to detect an OR ranging from 1.6-1.7 for a binary predictor prevalent in 30-50% of subjects.

We will also have to adjust for clustering by site in most of the analyses below.

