Hypothesis 2A & 2B: To evaluate difference in subjects' self-care competency, Wallston scores will be compared between intervention and control groups using the Wilcoxon Rank Sum test. Any repeat ED use and the number of ED visits during the 30-day follow up period will be compared between intervention and control groups using the Chi-square test and ANOVA as appropriate. To adjust for potential baseline differences between intervention and control subjects, a multiple logistic regression model will be constructed with repeat ED use as the dependent variable, study intervention group as the primary independent variable, and any covariates that were found to be imbalanced at baseline in our bivariate analyses. Multicollinearity between predictor variables will be assessed using multiple correlations (variance inflation factors). We will use the log likelihood ratio to assess overall model fit. We will also check for overdispersion and use Generalized Estimating Equation (GEE) to provide robust estimates of standard errors. Possible interaction effects between the covariates will be inspected and stratified analyses will be performed if there are significant interaction effects. Standard diagnostic measures for logistic regression such as Pearson residual and deviance residual will be used to check the goodness-of-fit of the regression model assumptions and identify any outliers.

Hypothesis 2C: The proposed economic assessment considers the financial costs and benefits of the CTI. Consistent with standard terminology,⁷³ we define *financial benefits* for this study as the consequences of the CTI that are related to health services cost, expenses, salaries, revenues, and other fiscal issues. It is important to recognize that adoption of the CTI will include both fixed (e.g., implementation) and variable (e.g., dependent on units of care delivered/patients served) costs. Dissemination of the program will require additional resources to cover CTI implementation. Hence, we

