Missing Data: Inference based on the proposed method is valid provided that missing data follows the missing completely at random (MCAR) assumption. However, the occurrence of missing data may depend on the observed response and such as missing at random (MAR) mechanism will generally bias the estimates. Sensitivity analysis will be performed to examine the MCAR assumption. If it is deemed to be severely violated, we will report treatment effects using weighted GEE that addresses the MAR mechanism.^{74,75} Biased estimates may arise if missing data does not follow the MAR mechanism, or non-ignorable non-response (NINR). Although unanticipated in this study, we will examine this potential NINR using the mixture model approach.⁷⁶

Future Planned Analysis: We are requesting to retain the data in an identified form for 10 years after completion of this study for future analyses of health care utilization and claims data from subjects' health insurance providers so as to understand if a paramedic coach reduces health care use and costs. We will keep the deidentified data indefinitely.

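### For the survey-only outcomes, the default analysis is one the plan calls valid under MCAR, and the switch to a MAR method hangs on an undefined judgement made after the data are seen

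*Combined protocol and SAP*

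**What the plan says.** Section 12.2 states the condition for its own methods: "Inference based on the proposed method is valid provided that missing data follows the missing completely at random (MCAR) assumption". It goes on to accept that missingness may follow observed data and that estimates are then generally biased. A sensitivity analysis is to examine MCAR, and on a bad result the reported analysis changes: "If it is deemed to be severely violated, we will report treatment effects using weighted GEE that addresses the MAR mechanism". A mixture model is held in reserve for non-ignorable non-response (NINR), which the plan does not anticipate.

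The methods this paragraph covers are set out earlier in the same section. They are chi-square tests with optional logistic models for 1A and 1B, a Wilcoxon rank sum test on the Wallston score for 2A, and a t-test for FCAT. For the primary outcome, "Any repeat ED use and the number of ED visits during the 30-day follow up period will be compared" by chi-square and ANOVA, followed by a logistic model adjusted for covariates found imbalanced at baseline. No imputation or weighting is part of any of these, so by default they run on observed cases.

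Section 12.1 says: "We anticipate approximately 25% attrition over the 30-day follow up period". That figure is given for the sample size of hypothesis 2B. There is no separate figure for day 4 or for caregivers.

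**The concern.** The plan names a likely defect in its default analysis and keeps that analysis as the default. The remedy depends on a word with no test, threshold, timing or decision-maker attached, and it is applied once the data can be seen. Two analysts could report different main results from the same data and both be following the plan.

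The switch can also change what is estimated. For 2A it would replace a rank test with a GEE treatment effect. The fallback is itself incomplete, because no covariates are named for the weights. Table 2 lists red-flag understanding and medication changes at day 4 only, so there is no earlier response to weight on and the weights must come from baseline data.

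MCAR is not an obvious starting point here. Section 4.3 deliberately keeps patients with impaired cognition or sensory limits. Section 3.2 says that cognition, depression, anxiety and isolation go with worse outcomes, and that patients admitted to a skilled nursing facility (put at under 2%) will not be surveyed. Only the intervention arm receives a home visit and up to three coach calls, so retention could differ by arm. None of this shows that it will.

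**Working it through.** **1. The plan's figures.** Inputs from section 12.1: 20% against 15%, two-sided 5%, 80% power, 860 per group, 25% attrition, 1200 per group recruited.

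- n = [1.96·√(2 × 0.175 × 0.825) + 0.842·√(0.20 × 0.80 + 0.15 × 0.85)]² / 0.05² = 906 per group. The stated 860 is not reproduced; it gives 77.9% power.
- 860 / 0.75 = 1147, but 1200 × 0.75 = 900, which gives 79.8% power.

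The gap between 860 and 906 is a separate matter. This point needs only the 25%, and hence 900 analysed per arm if all of that attrition is missing outcome data.

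**2. Stand-in outcome.** The documents give no expected proportion for 1A or 1B. I use 20% in both arms (no true effect) as an assumed binary outcome. The same sums then serve for ED use.

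**3. Missingness that depends on a baseline factor (MAR).** Assume 30% of patients are high-risk with a 34% event rate and the rest have 14%: 0.30 × 0.34 + 0.70 × 0.14 = 0.20. The control arm loses 25% at random. The intervention arm loses 40% of high-risk patients and 18.57% of the rest: 0.30 × 0.40 + 0.70 × 0.1857 = 0.25.

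- Retained in the intervention arm: 0.30 × 0.60 = 0.18 and 0.70 × 0.8143 = 0.57.
- Observed rate: (0.18 × 0.34 + 0.57 × 0.14) / 0.75 = 0.188.
- Spurious difference: 20.0 − 18.8 = 1.2 points. With 900 per arm the standard error is 0.0186, z = 0.64, and the rejection rate is about 10% instead of 5%.
- Weighting by the inverse of retention: (0.18 / 0.60) × 0.34 + (0.57 / 0.8143) × 0.14 = 0.20. The bias is removed.
- If both arms lose patients in this same pattern, both show 18.8% and the null difference is zero.

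**4. Missingness that depends on the outcome itself.** Let p be the true risk, m the fraction missing, and k the ratio of the chance of being missing with an event to that without. Then q0 = m / (kp + 1 − p), q1 = k·q0, and observed risk = p(1 − q1) / (1 − m). Selection is in the intervention arm only, and p = 0.20.

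| m | k | observed risk | bias (points) | rejection rate |
|---|---|---|---|---|
| 0.25 | 1.25 | 0.1873 | 1.3 | about 10% |
| 0.25 | 1.5 | 0.1758 | 2.4 | about 26% |
| 0.25 | 2 | 0.1556 | 4.4 | about 70% |
| 0.05 | 1.5 | 0.1962 | 0.4 | about 5.6% |

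For the last row: q0 = 0.05 / 1.1 = 0.0455, q1 = 0.0682, and 0.20 × 0.9318 / 0.95 = 0.1962. With k = 1.5 in both arms, both observed risks are equal and the null bias is zero.

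A MAR method removes none of the bias in this table unless baseline covariates explain the link between event and loss. Steps 3 and 4 are therefore the two ends: wholly recoverable and not recoverable.

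**The case against.** **The primary outcome is well protected, and this stands.** A reader might infer that 25% attrition puts the main ED-use result at risk. One could assume 20% against 30% attrition and a 35% risk in those lost: (0.20 − 0.20 × 0.35) / 0.80 = 0.1625 against (0.20 − 0.30 × 0.35) / 0.70 = 0.1357. That is 2.7 spurious points, about half the 5-point target. The documents do not support that reading. Section 3.2 and Table 2 take ED use from survey, Epic and administrative records, and section 12.2 takes events from both health systems' information systems. Section 4.2 requires a local PCP and county residence. Sections 3.2 and 7 continue record review for those who only stop contact (section 7 subject to permission). The 25% is a planning allowance, not a forecast that a quarter of ED-use values will be missing.

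**The check need not be weak, and this stands.** A reader might infer that a preliminary look at MCAR would miss moderate departures. With 1200 per arm, 22.5% against 27.5% attrition gives z = 0.05 / √(2 × 0.25 × 0.75 / 1200) = 2.8, or about 81% power; 20% against 30% gives z = 5.7. In step 3 both arms lose 25%, so comparing overall retention would show nothing, while comparing loss by baseline risk within arm could. The complaint is that the check is undefined, not that it lacks power.

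**The plan already limits the problem, and this stands in part.** Section 6.3 has blinded staff survey both arms, including patients in the ED or hospital when a survey is due. Logistic models tolerate missingness that depends on covariates they contain, so MCAR is stricter than they need. But their covariates are not chosen to predict missingness, and the unadjusted chi-square, Wilcoxon and t-tests have no such protection. Weighted GEE is itself an inverse-probability method, so the disagreement is about which analysis is primary, and when that is settled.

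**Conclusion.** The point holds for the survey-only outcomes: 1A and 1B at day 4, 2A and FCAT at day 30. None of these is the powered hypothesis. The plan reports by default an analysis whose stated condition it doubts, and it leaves the choice of the reported result to an undefined judgement on seen data. That is a defect whatever the bias turns out to be.

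The size is assumed throughout. With 25% missing and selection in one arm only, the examples give 1.2 to 4.4 points on a 20% outcome. They give zero for the null comparison if selection is equal in both arms. Day-4 losses may be below 25%. A MAR method recovers only the part explained by the covariates used, so it should not be presented as a cure for all attrition bias. For 30-day ED use the bias is likely small, about 0.4 points at 5% missing under 1.5-fold selection in one arm. Patients who ask for full expungement (section 7) leave no baseline data, so no method of this kind can reach them.

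**What to change.** Delete the conditional switch in section 12.2. For 1A, 1B, 2A and FCAT, name one MAR-valid method as primary, either multiple imputation or inverse-probability weighted GEE, and fix the estimated quantity for each outcome in advance. List the covariates: arm, site, caregiver stratum, cognition, comorbidity, depression, health literacy, prior ED use and, where measured, the baseline PHCS or FCAT score. Keep complete-case results and the NINR mixture model as sensitivity analyses.

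For 30-day ED use, state when a value counts as missing after record review, and apply the same method to what remains. Say in section 12.1 how much of the 25% is expected to be missing ED-use data, so that it agrees with the record follow-up in sections 3.2 and 7.

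The cost is plan wording and modest extra programming. Table 2 already collects the patient covariates and both baseline scores in the ED. The downside is reliance on an imputation or weight model, which the complete-case results will help readers assess.

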12.3 DATA AND SAFETY MONITORING

The data safety and monitoring plan should be commensurate with the risks of the study, as well as the size and complexity of the study. This plan includes monitoring procedures with structured adverse event (AE) and serious adverse event (SAE) determination, monitoring and reporting systems with standardized protocols and forms for referring and/or treating study participants who experience adverse events. AEs should be reported to the IRB, the NIA Program Officer.

1.0 PARTICIPANT SAFETY

1.1 Potential Risks and Benefits for Participants

Potential Risks

The potential subject risks associated with this study are as follows:

1. Stress caused by the survey questions or assessments: Either through the questions themselves or frustration or fatigue from completing the questions, this risk will be present. Although we anticipate this risk, it is expected to be commensurate with what participants would experience outside of the research study because the questions are standard questions asked by health care providers. However, the risk can be mitigated and made less likely by taking appropriate steps described in the "Protection Against Risk" section 1.3 below.
2. Identification of issues of depression or suicidality: Through the survey instruments, depression or suicidality may be identified. Identification of these issues would require contacting the appropriate individuals for intervention, such as the ED provider or the health care team.
3. Identification of abuse or neglect: Home visits will occur as part of this study and abuse or neglect may be observed during a visit. We are required by state law to report this to the appropriate authorities. This may include reporting to local law enforcement or protective service agencies, resulting in legal or social risks to subjects or other members of their household. This risk is disclosed in the consent document.
4. Release of confidential information: Through the surveys and assessments and medical record reviews, confidential information will be collected. Release of identifiable information outside the study team presents a potential risk of social or psychological harm. However, the risk for this is extremely unlikely due to the procedures used to mitigate this issue that are described in the "Protection Against Risk" section and we are not collecting sensitive information about participants.
5. Referral to primary care or ED provider: Based on the findings of the study, we may refer subjects to their primary care or an ED provider. Acceptance of this referral will be dependent on the subject, but this referral may occur, leading to further evaluation of health conditions. This referral may result in added costs to the subject.
6. Incorrect delivery of the intervention: If the Care Transitions Intervention is delivered incorrectly, a result may be an increased use of ED or hospital services. That would include increased cost and a burden on subjects. Although we anticipate this risk, it is expected to be commensurate with what participants would experience outside the research study when they receive the Care Transitions Intervention as part of their care.
7. Risk of delayed medical care: With the enrollment of subjects in the ED, there is a chance that medical care could be delayed due to the enrollment process. This risk is somewhat limited due to the planned process, which includes communication with care team who will not be able to determine if the patient will be discharged home until critical medical care is complete. However, it must be monitored.

Potential Benefits

The services provided through this study may have benefits as follows:

1. Identification of unrecognized medical conditions: Through the research protocol, medical conditions not recognized by the subject may be identified. For instance, depression, medication errors, or development of acute medical problems may be identified and then receive care either through the coaching of the patient/caregiver or through notification of the patient's primary care provider / ED provider.
2. Health education: Through the coaching provided, patients may better understand their health, develop better processes to manage their health, and even experience better health.

1.2 Adverse Event, Serious Adverse, Unanticipated Problem Event Collection and Reporting

The research team will use the NIA approved definitions of adverse event (AE) and serious adverse events (SAE). These definitions are as follows:

Adverse Event

Definition: Any untoward or unfavorable medical occurrence in a human study participant, including any abnormal sign (e.g. abnormal physical exam or laboratory finding), symptom, or disease, temporally associated with the participants' involvement in the research, whether or not considered related to participation in the research.

Examples of AEs for this study include:

- Stress from completion of the survey instruments
- ED visit without hospitalization or other SAE criteria (below)
 - Note: a repeat ED visit without hospital admission occurs in up to 20% of older adults who have an index visit. Given the high incidence of this event (up to 20%) and the fact that it does not meet the NIA's definition of a SAE, we are considering it an AE, not a SAE.

Serious Adverse Event

Any adverse event that:

- Results in death
- Is life threatening, or places the participant at immediate risk of death from the event as it occurred
- Requires or prolongs hospitalization
- Causes persistent or significant disability or incapacity
- Results in congenital anomalies or birth defects
- Is another condition which investigators judge to represent significant hazards

Unanticipated Problem (UP)

This is any incident, experience, or outcome that:

- Is unexpected, in terms of nature, severity, or frequency, given (a) the research procedures and (b) the characteristics of the study population;
- Is related or possibly related to participation in the research (i.e., reasonable possibility that the incident, experience, or outcome may have been caused by the procedures involved in the research);
- Suggests that the research places participants or others at a greater risk of harm (including physical, psychological, economic, or social harm) than was previously known or recognized.

Event Collection

Events for investigation will be collected through three mechanisms:

1. During research activities, any voluntary responses that identify an AE or SAE will be flagged by study staff for review.
2. During research activities, there will also be a systematic collection of AEs and SAEs. As part of the chart review at UW, we will be collecting death, hospitalizations, ED use, and health care utilization. Furthermore, through patient/caregiver surveys we will be collecting the same

information to particularly identify death, hospitalization, ED use, and health care utilization at non-UW facilities. These AEs and SAEs will be flagged by study staff for review.

3. Independent notification, such as through an unsolicited letter or telephone call, of any events that meet AE or SAE criteria will be flagged by study staff for review.

For each of these events, the staff will record a brief description of the experience, the date of onset, the date of resolution, severity, expected, relationship to study treatment, and outcome of this event. The research team will utilize the NIA approved flow sheets and forms to identify and track potential AEs and SAEs.

Events will be reviewed (within one business day of collection) to determine if they meet criteria for an AE or SAE, as well as whether the AEs/SAEs are UP. Depending on the categorization, the following review will occur (See Figure 1):

Any AE will be reviewed within 5 business days of categorization (as above):

1. The information regarding the subject will be accessed and the NIA tracking form will be completed.
2. The site PI designee (who must be a clinician with relevant expertise) will be notified to determine if the event is unexpected, related to participation in the research, or places participants at a greater risk of physical or psychological harm than was previously known or recognized.
3. If the AE is related but expected, then the PI will report the event to the Independent Safety Officer and the NIA with the monthly reports.
4. or not unexpected, then the PI will report the event to the Independent Safety Officer and the NIA with the monthly reports.
5. If the AE is unexpected, the governing IRB will be notified within 10 business days of categorization.
 - a. The other site investigators will be notified promptly for report to their IRB.
6. The event will be discussed on the weekly study oversight call.

Any SAE will be reviewed within 1 business day of categorization (as above):

1. The information regarding the subject will be accessed and the NIA tracking form will be completed.
2. The site PI designee (who must be a clinician with relevant expertise) will be notified to determine if the event is unexpected, related to participation in the research and places participants at a greater risk of physical or psychological harm than was previously known or recognized.
3. The overall PI will be notified without unblinding the PI.
4. The NIA and Independent Safety Officer will be notified within 1 business day of categorization.
5. The governing IRB will be notified within 1 business day if the SAE constitutes an UP and is immediately life-threatening or severely debilitating to other participants.
6. If it is unexpected, related, or possibly related, the other study investigators and sites will be notified promptly.
7. The PI will provide a final update to the NIA and Independent Safety Officer within 14 business days of the event for all SAE cases, unless the investigation is still ongoing.
8. The event will be discussed on the weekly study oversight call.

Grading Criteria

We will utilize the NIA approved grading criteria, as indicated on the event forms including:

Severity

- 1 = Mild- Awareness of signs or symptoms, but easily tolerated and are of minor irritant type causing no loss of time from normal activities. Symptoms do not require therapy or a medical evaluation; signs and symptoms are transient.
- 2 = Moderate- Events introduce a low level of inconvenience or concern to the participant and may interfere with daily activities, but are usually improved by simple therapeutic measures; moderate experiences may cause some interference with functioning
- 3 = Severe- Events interrupt the participant's normal daily activities and generally require systemic drug therapy or other treatment; they are usually incapacitating

Study Relatedness

- 1 = Definitely related- The adverse event is clearly related to the study procedure – i.e. an event that follows a reasonable temporal sequence from administration of the study intervention, follows a known or expected response pattern to the suspected intervention, that is confirmed by improvement on stopping and reappearance of the event on repeated exposure and that could not be reasonably explained by the known characteristics of the subject's clinical state.
- 2 = Possibly related- An adverse event that follows a reasonable temporal sequence from administration of the study intervention follows a known or expected response pattern to the suspected intervention, but that could readily have been produced by a number of other factors.
- 3 = Not related- The adverse event is clearly not related to the study procedure - i.e. another cause of the event is most plausible; and/or a clinically plausible temporal sequence is inconsistent with the onset of the event and the study intervention and/or a causal relationship is considered biologically implausible.

Expectedness

- Unexpected - nature or severity of the event is not consistent with information about the condition under study or intervention in the protocol, consent form, or relevant research literature.
- Expected - event is known to be associated with the intervention under study.

Event Actions

As a result of the event and the event investigation, a number of different actions may occur, including the following:

- Changes to the protocol
- Modification of consent documents
- Additional training of study staff
- Termination of the study

[figure not shown]
As these changes are occurring, the study may need to be stopped. This study will use the following stopping rule:

In the event that a SAE is unexpected and related to the research processes, new enrollment and interventions will be halted but ongoing follow up procedures will continue. This level of intervention is justified because the follow up is a brief survey of health status and satisfaction and lacks any intervention. This decision will be confirmed with the Independent Safety Officer, the UW-IRB, and the NIA.

Once the event has been investigated, then the study team, in conjunction with the Independent Safety Officer, will determine if the event actions proposed are sufficient to address the SAE that was unexpected. Once it has been sufficiently addressed and approved by the governing IRB, then the study will be restarted.

Figure 1

Serious Adverse Event/Adverse Event/Unexpected Problem Process Flow

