8. SAFETY AND REPORTABLE EVENTS

The level of risk in this supportive care behavioral intervention is low, and no published literature regarding this widely implemented intervention has reported any problems. All research team members will be involved in safety monitoring.

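### Appendix A 1.2 tests relatedness in two ways and the halting rule does not say which applies; on the graded scale a new kind of serious harm fits no related grade

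*Combined protocol and SAP*

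**What the plan says.** The stopping rule, under Event Actions in Appendix A 1.2, reads: "In the event that a SAE is unexpected and related to the research processes, new enrollment and interventions will be halted". Follow-up continues, and the decision is confirmed with the Independent Safety Officer, the UW IRB and the NIA. Appendix A 2.0 plans no interim analysis, so no other halting rule has a defined trigger.

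The terms are defined earlier in Appendix A 1.2:

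- **Definitely related** needs an event that "follows a known or expected response pattern to the suspected intervention, that is confirmed by improvement on stopping and reappearance of the event"; the reappearance must come after a further exposure.
- **Possibly related** needs an event that "follows a known or expected response pattern to the suspected intervention, but that could readily have been produced by a number of other factors".
- **Not related** opens with "The adverse event is clearly not related to the study procedure". It is then explained by three alternatives: another cause is most plausible, the timing does not fit, or causation is biologically implausible.
- **Expected** means that the "event is known to be associated with the intervention under study". **Unexpected** is judged on whether the nature or severity departs from what the protocol, consent form or literature describes.
- The **unanticipated-problem definition** covers events related or possibly related to participation. It explains this as a reasonable possibility that the research procedures caused the event, and it requires no known pattern.

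In the SAE review steps, step 2 has a clinician judge whether the event is unexpected and related to participation. Step 6 lists related and possibly related as separate categories.

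**The concern.** A rule that halts on unexpected and related events is there to catch harm that nobody foresaw. If an event can be graded related only when it follows a pattern already known or expected, the two halves of the rule pull against each other. Protocol section 8 says that "no published literature regarding this widely implemented intervention has reported any problems", so the documents describe few patterns beyond the risks listed in Appendix A 1.1.

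What is at stake is whether enrolment and the intervention pause when a new serious harm appears. Two reviewers, or the two sites, could read the same text and reach opposite decisions on the same event. The same gradings also fill the expectedness and relationship columns of the by-arm SAE listing in the report templates, so the ambiguity carries into what the safety officer and the NIA see.

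**Working it through.** No arithmetic applies. The check takes each kind of SAE through the definitions under the three meanings that the rule's word *related* could carry.

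**Inputs, all from Appendix A 1.2:** the stopping rule (Event Actions), the three relatedness grades (Study Relatedness), the two expectedness definitions (Expectedness), the relatedness test in the unanticipated-problem definition, and SAE review steps 2 and 6.

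**Step 1: a new kind of SAE, well timed, plausibly caused, with no better explanation.** It is unexpected by nature. It has no known or expected response pattern, so it fails both related grades. It also meets none of the three alternatives under not related. On the printed scale it has no grade. Under the unanticipated-problem test it is related.

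**Step 2: a known kind of SAE at its known severity.** It can be graded related, but it is expected. The rule is not met on any reading.

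**Step 3: a known kind of SAE at unexpected severity.** It is unexpected and can be graded possibly related. To be definitely related it must also be "that is confirmed by improvement on stopping and reappearance of the event on repeated exposure". A death cannot show that. A non-fatal event could in principle, because the intervention is one home visit and up to three calls, but that is little exposure on which to show it.

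**Step 4: an SAE that is clearly unrelated.** The rule is not met on any reading.

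| Kind of SAE | Related = definite grade only | Related = definite or possible grade | Related = reasonable possibility |
|---|---|---|---|
| New kind, plausibly caused | Not met | Not met | Met |
| Known kind, known severity | Not met | Not met | Not met |
| Known kind, unexpected severity | Not met for a death; hard to meet otherwise | Met | Met |
| Clearly unrelated | Not met | Not met | Not met |

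The readings disagree in two of the four rows. The first row depends on which test applies. The third depends on whether possibly related counts. The rule's text settles neither. Step 6 names possibly related alongside related, which leaves open that the rule, naming only related, means the higher grade alone. The unanticipated-problem definition points the other way.

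**The case against.** The strongest reply is that the rule cites no grade. It speaks of the research processes, whereas the grades speak of the study procedure and intervention. SAE review step 2 uses the language of participation in the research, which is also the language of the unanticipated-problem definition. Read that way, a novel and plausibly caused SAE does trigger the halt. This is a fair reading, and the process-flow figure, which might settle it, is not in the available text. It shows that the conflict is unresolved, not that it is absent.

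The other safeguards are also real. Every SAE goes to the NIA and the safety officer within 1 business day and to the weekly call. Monthly reports compare the groups. The safety officer may recommend termination, and termination is a listed event action. None of these depends on the relatedness grade, but all are matters of judgement and do not make the stated rule work.

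A reader might infer several stronger points that the documents do not support:

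- *A related event is expected by definition, so the rule can hardly ever fire.* Unexpected severity remains a route. Most risks in Appendix A 1.1 are described as non-serious, so a death arising from one could qualify. A response pattern is also not quite the same thing as a listed event.
- *Re-exposure never occurs.* Coaching contacts repeat within a participant. The point is firm only for death.
- *The listed risks are the only known patterns.* Expectedness also refers to the consent form and the literature, which cannot be checked here.
- *Excess ED or hospital use escapes because Unexpected omits frequency.* The unanticipated-problem definition does say "Is unexpected, in terms of nature, severity, or frequency", but the halting rule is triggered by a single SAE. Frequency is an aggregate matter that the monthly by-arm reports address. An ED visit that meets no SAE criterion is classed as an AE and could not trigger the rule under any definition.

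**Conclusion.** The concern holds as an unreconciled conflict of definitions. Appendix A 1.2 carries two tests of relatedness, and the only halting rule with a defined trigger does not choose between them or say whether possibly related counts. If the printed grades govern, a new kind of plausibly caused SAE fits no related grade, and the rule is met essentially only by a known kind of event of unexpected severity. If the reasonable-possibility test governs, the rule can catch new harms.

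The consequence described for the printed grades assumes that the rule's *related* is the graded term defined just before it. That is a natural reading, but not the only one. It also takes the known-or-expected-pattern condition literally. The intervention is described as low risk and the discretionary safeguards are substantial, so this should be fixed but does not threaten the trial's validity.

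**What to change.** In Appendix A 1.2, reconcile the unanticipated-problem definition, the relatedness grades, the expectedness definitions, SAE review steps 2 and 6, and the stopping rule. Relatedness should be judged independently of expectedness, and every SAE should fit exactly one grade. The plan's own reasonable-possibility wording is available for this. The improvement-and-reappearance condition in the definite grade should be reviewed in the same pass, since a death cannot meet it.

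The sponsor, safety officer, NIA and IRB should then state in the rule which relatedness grades it uses. This review does not say which they should be. The event form, the SAE listing template and the process-flow figure should follow the same definitions.

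The cost is a wording and form amendment. The grading criteria are described as NIA approved, so NIA and IRB review will be needed, not just notification. A few more events may be graded possibly related and need discussion with the safety officer. Sample size, data collection and the efficacy analysis are unaffected.
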